7.5.5 Treatment related haematological Adverse Events

For any treatment related haematological toxicities (e.g. Neutrophil or platelet count decreases) delay avelumab treatment for a week until the event resolves to baseline. If the toxicity has not resolved with 1 week delay please check with trials office if continued treatment is recommended.

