7.2 Treatment Schedule

Avelumab 10 mg/kg will be administered once every 14 days for a proposed duration of 8 cycles (28 day cycles), (16 doses).

If the patient is showing clinical benefit following 8 cycles of trial treatment patients may continue to receive avelumab treatment at the treating Investigator's discretion, until loss of response, toxicity, or death.

Every effort should be made for patients to attend on the scheduled visit days. However, if a patient is unable to attend on the specified day, assessments may be scheduled for +/- 3 days.

The full blood count should be assessed prior to each treatment (within 24 hours of treatment) to ensure the following criteria are met:

- Platelets $> 75 \times 10^9/L$
- Neutrophils $> 1.0 \times 10^9/L$
- Bilirubin $< 1.5 \times ULN$
- Creatinine clearance (CrCL) (Cockcroft-Gault) $\geq 30 \text{ ml/min}$.
- ALT/AST $\leq 1.5 \times ULN$ on Cycle 1 day1; thereafter $\leq 3 \times ULN$

Please also refer to Section 7.5 for dose delays and modifications, and to section 7.7 for concomitant medications.

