7.8 Patient Treatment Discontinuation

In the event of discontinuation of study treatment, e.g. completing treatment, unacceptable toxicity or patient choice, full details of the reason/s for discontinuation should be recorded on the appropriate pages on the CRF. All patients, including non-compliant patients, should be followed up according to the protocol unless they withdraw specific consent. Patients who stop treatment due to adverse experiences (clinical or laboratory) will be treated and followed according to accepted medical practice. All pertinent information concerning the outcome of such treatment must be recorded in the CRF.

The following are justifiable reasons for the Investigator to stop study treatment:

- unforeseen events: any event which in the judgement of the Investigator makes further treatment inadvisable
- serious violation of the study protocol (including persistent patient non-attendance and persistent non-compliance)
- stopping by the Investigator for clinical reasons not related to the study drug treatment

Patients must stop study treatment in the event of:

- unacceptable toxicity (detailed below)
- SAE requiring permanent discontinuation of treatment
- the patient becoming pregnant
- Disease Progression

Table 5. Adverse Events requiring avelumab discontinuation or modification

Any Grade 4 AEs

 • except for single laboratory values out of normal range that are unlikely related to study treatment as assessed by the Investigator, do not have any clinical correlate, and resolve within 7 days with adequate medical management
Any Grade 3 AEs except for any of the following:

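### Sections 7.5.5 and 7.8/Table 5 give incompatible instructions for treatment-related haematological events, with no cross-reference or precedence

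*Combined protocol and SAP*

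**What the plan says.** Section 7.5.5 covers treatment-related haematological events without a grade limit, with neutrophil and platelet falls as its examples. It tells sites to "delay avelumab treatment for a week until the event resolves to baseline". It then says: "If the toxicity has not resolved with 1 week delay please check with trials office if continued treatment is recommended". Continuing treatment therefore stays open.

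Section 7.8 lists events for which patients must stop study treatment. One is unacceptable toxicity, with the detail in Table 5. The table's first row is any Grade 4 adverse event, "except for single laboratory values out of normal range that are unlikely related to study treatment as assessed by the Investigator", with further conditions on clinical correlate and resolution. The second row is any Grade 3 adverse event outside a list of exceptions. The laboratory exception in that list has the same causality condition. Table 5 then gives separate rules for Grade 2 events, with exemptions for infusion-related reactions and for hormone insufficiencies.

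Section 7.2 sets pre-dose criteria: "The full blood count should be assessed prior to each treatment (within 24 hours of treatment) to ensure the following criteria are met". These include a platelet count above 75 and a neutrophil count above 1.0 (both ×10⁹/L). It goes on: "Please also refer to Section 7.5 for dose delays and modifications".

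**The concern.** A site with a treatment-related count fall has to look in two places, and for the more severe grades the two give different answers. One site may delay and, after asking the trials office, resume. Another may take the patient off treatment. Both would be following the protocol.

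Three things are at stake. The first is patient safety, because it is unclear whether further dosing is allowed. The second is exposure over the 8 cycles in which the primary response endpoint is measured, which would vary with the page a site reads. The third is the discontinuation data, where the reason and timing of stopping would partly reflect interpretation. Blood counts are checked before every dose, so the question can come up repeatedly for the same patient.

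**Working it through.** No figure in the plan bears on this, so the check is a comparison of rules for the same event, taken from sections 7.2, 7.5.5, 7.8 (Table 5) and 8.1.1.

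**Step 1. Do both rules reach the same event?** Section 8.1.1 treats a laboratory abnormality as an adverse event only in stated cases, one being that it requires interruption of the study drug. Section 7.5.5 is headed as dealing with adverse events and its action is a delay. On the protocol's own terms, an event handled under 7.5.5 is an adverse event, so Table 5 also applies to it.

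**Step 2. Can the laboratory exceptions rescue it?** No. Section 7.5.5 covers only treatment-related toxicity, while both exceptions in Table 5 (Grade 4 and Grade 3) require that the value be unlikely to be related to treatment. No event can satisfy both conditions.

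**Step 3. Compare by grade.**

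| Treatment-related count fall | 7.5.5 | 7.8 / Table 5 |
|---|---|---|
| Grade 3 or 4 | Delay; if unresolved after a week, ask the trials office about continuing | Must stop |
| Grade 2, recovery target | Baseline | Grade 1 or lower |
| Grade 2, unresolved | 1-week delay, then ask the trials office | From the end of the current cycle, omit the following cycle; permanent discontinuation if still unresolved at its end |
| Grade 2, second occurrence of the same event | Delay, as for the first | Permanent discontinuation; no haematological exemption |
| Grade 1 | Delay | No row |

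A cycle is two fortnightly infusions, so omitting a cycle is a longer interruption than a 1-week delay.

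**Step 4. Can both be obeyed at once?** For Grade 3 or 4, no: stopping leaves nothing for the delay-and-ask route to do. The same holds for a second Grade 2 occurrence. The Grade 2 recovery targets alone could be combined by taking the stricter, because Table 5 says only that treatment may continue at Grade 1 or lower. For Grade 1 there is no conflict.

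**Step 5. Is precedence stated?** No. Table 5 refers to Table 3 for infusion-related reactions but nowhere to 7.5.5, and 7.5.5 does not mention Table 5.

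**Step 6. Is 7.2 a further conflict?** No. It lists counts that must be met before dosing; it does not instruct sites to dose once they are met, and it sends the reader to 7.5. Sections 7.2 and 7.5.5 can be applied together. What remains is an unexplained difference: absolute floors in one, return to baseline in the other.

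No CTCAE cut-off is needed for any of these steps.

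**The case against.** The strongest case against is that Table 5 is less absolute than it looks. Its title speaks of discontinuation or modification, and its Grade 3 and 4 rows do not use the word permanent, whereas the Grade 2 rules do. Table 4 lets Grade 3 colitis, rash, creatinine increase and other immune-related events be withheld and resumed. If Table 5 means a stop for every non-excepted Grade 3 event, it clashes with much of 7.5. On this view the event-specific rules in 7.5 are meant to govern and Table 5 is a general backstop.

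That is a reasonable guess at the intent, and it shows that the ambiguity is wider than blood counts. It does not remove the conflict. The lead-in says patients must stop and lists toxicity beside pregnancy and disease progression. The Grade 3 and 4 rows give no general restart condition. Table 5 specifically exempts a first Grade 3 infusion-related reaction that qualifies for continued therapy under Table 3, which is needed only if the default is not to continue. No sentence says that 7.5 takes precedence.

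A second objection is that Step 1 is circular: a fall becomes an adverse event because 7.5.5 interrupts treatment for it. This has some force for small falls, where it may be unclear whether 7.5.5 is triggered at all. It does not help for Grade 3 or 4, since any event that 7.5.5 governs is one it calls an adverse event.

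A reader might also infer two stronger points. One is that 7.2, 7.5.5 and Table 5 give three incompatible instructions, so that the same patient could be dosed, delayed or stopped. Step 6 shows why the text does not support this. The other is that 7.5.5 sets two contradictory durations, a week and until recovery. The wording is awkward, but its next sentence largely settles the procedure by sending unresolved cases to the trials office after one week.

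**Conclusion.** The point stands as a two-way conflict between 7.5.5 and 7.8/Table 5. It is direct for treatment-related Grade 3 or 4 count falls and for a second occurrence of the same Grade 2 event. For a first Grade 2 event the rules differ in recovery target and in the length and consequence of interruption. It does not extend to every count fall, and 7.2 is not part of the contradiction.

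The size cannot be derived, because the frequency of these events in this population is not given. For rough scale on the severe grades only, section 1.2.3 reports 59 of 480 patients (12.3%) with treatment-related events of all types at the highest grades. The text prints this as above grade 3; taken here, as an assumption, to mean Grade 3 or higher, and with section 1.2.2's assumption that the solid-tumour safety profile carries over, it gives 0.123 × 30 ≈ 3.7 patients, or 0.123 × 35 ≈ 4.3. Haematological events would be only part of that: anaemia and lymphocyte decrease are in the list, while neutrophil and platelet falls are not. Grade 2 events are not counted in it.

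Few patients may be affected, but the design is sensitive to single patients. In Appendix 2, moving from 11 to 12 responses in 30 raises the probability that the response rate exceeds 35% from 60% to 74%. Whether stopping or resuming would change any patient's best response is unknown. This is a consistency and safety-wording defect that should be corrected, not a threat to the design.

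**What to change.** In one amendment, reconcile 7.5.5 with 7.8/Table 5 and state which of them governs treatment-related haematological events at each grade, including recurrent Grade 2 events. Add a cross-reference in each direction and one from 7.2, with a sentence on how the pre-dose floors in 7.2 relate to the return-to-baseline target in 7.5.5. The same edit could clarify whether the Grade 3 and 4 rows of Table 5 mean a stop or a modification, since the title and the lead-in differ. The clinical content of the rule is for the investigators and sponsor; none is proposed here.

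The cost is a wording change, with no effect on sample size, endpoints or analysis. The amendment log shows that Table 5 has already been aligned with Table 3 in this way. If patients have already been managed under the present text, the reason recorded for each haematological delay or stop should be checked when the discontinuation data are summarised.

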7.5.6 Drug Induced Liver Injury (Hy's law cases)

The threshold of laboratory abnormalities for a potential Drug Induced Liver Injury case depends on the patient's individual baseline values and underlying conditions. Patients who present with the following laboratory abnormalities should be evaluated further as potential Hy's law cases to definitively determine the etiology of the abnormal laboratory values:

-Subjects with AST/ALT and Bilirubin baseline values within the normal range who subsequently present with AST OR ALT values $>3 \times$ ULN AND a Bilirubin value $>2 \times$ ULN with no evidence of hemolysis and an alkaline phosphatase value $<2 \times$ ULN or not available;

-For subjects with baseline AST OR ALT OR Bilirubin values above the ULN, the following threshold values are used in the definition mentioned above, as needed, depending on which values are above the ULN at baseline:

- Preexisting AST or ALT baseline values above the normal range: AST or ALT values >2 times the baseline values AND $>3 \times$ ULN; or $>8 \times$ ULN (whichever is smaller).
- Preexisting values of Bilirubin above the normal range: Bilirubin level increased from baseline value by an amount of at least $1 \times$ ULN or if the value reaches $>3 \times$ ULN (whichever is smaller).

If a Hy's law case is confirmed this must be reported to the trials office as an SAE. Patients should be treated as in Table 4 above.

7.6 Treatment Compliance

Non-compliance is not likely to be an issue as patients must attend hospital to receive infusions of avelumab. Pharmacy departments will be required to maintain accurate records of drug accountability. For further information please see the pharmacy manual.

7.7 Concomitant Medication

Primary prophylactic use of granulocyte-colony stimulating factors is permitted during the study. They may also be used to treat treatment emergent neutropenia as indicated by local guidelines.

Use of erythropoietic growth factors is allowed during the study.

Patients are prohibited from receiving the following therapies during the treatment phase of this trial:

- Anti-cancer systemic chemotherapy or biological therapy
- Immunotherapy not specified in this protocol
- Investigational or experimental agents other than avelumab
- Radiation therapy (with the exception of Palliative radiotherapy to specific sites of disease considered medically necessary by the treating physician. All attempts should be made to rule out disease progression in the event of increased localized pain. If palliative radiotherapy is needed to control bone pain, the sites of bone disease should be present at baseline, otherwise, bone pain requiring radiotherapy will be considered as a sign of disease progression.).
- Immunosuppressive drugs, unless otherwise indicated for the treatment of AEs (see Tables 3 and 4). See below Clarification about Steroid Use.
- Any vaccine therapies for the prevention of infectious disease (eg, human papilloma virus vaccine) except for inactive vaccines (e.g. the flu vaccine).
- Herbal remedies with immune-stimulating properties (eg, mistletoe extract) or known to potentially interfere with major organ function (eg, hypericin).

Clarifications about Steroid Use: Data indicate that corticosteroids have an adverse effect on T cell function and that they inhibit and damage lymphocytes.

Therefore, the use of steroids during this trial is restricted as follows:

- Therapeutic use: for the treatment of infusion-related reactions and short-term treatment of AEs, steroids are permitted according to the modalities indicated in table 3 and 4
- Physiologic use: steroid replacement for adrenal insufficiency at doses equivalent to ≤ 10 mg prednisone daily is acceptable.
- Prophylactic use (eg, for the prevention of acute infusion-related reactions): is prohibited – unless otherwise indicated in Table 3

There are no prohibited therapies during the Post-Treatment Follow-up Phase.

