7.3 Assessments

Table 2. Schedule of Assessments

Parameter	Screening (28 days unless otherwise stated)	Cycle 1		Cycle 2		Cycle 3		Cycle 4		Cycle 5		Cycle 6		Cycle 7		Cycle 8		Subsequent cycles		End of Treatment /Progress ion	12 month Follow- up (from treatment start)	16 month Follow- up (from treatment start)	20 month Follow- up (from treatment start)
		Day 1	Day 15	Day 1	Day 15	Day 1	Day 15	Day 1	Day 15	Day 1	Day 15	Day 1	Day 15	Day 1	Day 15	Day 1	Day 15	Day 1	Day 15				
Informed consent	X																						
Medical History	X																						
Pregnancy test (if applicable)	X	X		X		X		X		X		X		X		X		X		X			
Prior Diagnosis/ Prior Treatment / baseline conditions	X																						
ECOG performance status	X	X		X		X		X		X		X		X		X		X		X			
Height (pre-study only)	X																						
Weight	X	X		X		X		X		X		X		X		X		X					
Diagnostic tissue biopsy (within 3 months of registration)	X																			X (optional)			
Bone Marrow Trehpine biopsy (within 3 months)	X																			X ¹			
Laboratory Tests (Haematology ² and Biochemistry ³)	X ⁴	X	X	X	X	X	X ⁴	X	X	X	X	X	X	X	X	X	X	X	X ⁴				
Virology (HIV, HBV, HCV)	X																						
Urinalysis (protein, glucose)	X	X		X		X		X		X		X		X		X		X		X			

Parameter	Screening (28 days unless otherwise stated)	Cycle 1		Cycle 2		Cycle 3		Cycle 4		Cycle 5		Cycle 6		Cycle 7		Cycle 8		Subsequent cycles		End of Treatment /Progression	12 month Follow-up (from treatment start)	16 month Follow-up (from treatment start)	20 month Follow-up (from treatment start)
		Day 1	Day 15	Day 1	Day 15	Day 1	Day 15	Day 1	Day 15	Day 1	Day 15	Day 1	Day 15	Day 1	Day 15	Day 1	Day 15	Day 1	Day 15				
and blood)																							
ACTH, Thyroid function (T4 & TSH), tests for pancreatitis		X				X				X					X					X			
ECG (single 12 lead)	X	X ⁵		X ⁵																X			
Clinical Disease assessment / physical exam	X	X		X		X		X		X		X		X		X		X		X	X	X	X
CT scans with IV contrast NCAP	X					X ⁶						X ⁶				X ⁶		X ⁷	X ⁸	X	X	X	X
Avelumab 10mg/kg every 2 weeks		X	X	X	X	X	X	X	X	X	X	X	X	X	X	X	X	X					
Concomitant Diseases and Treatment		<< Ongoing assessment until 28 days after treatment discontinuation >>																					
Adverse Events		<< Ongoing assessment until 28 days after treatment discontinuation >>																					
Blood samples collected for research	X				X				X				X				X		X ⁷	X	X	X	X

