7.9 Patient Follow Up

All patients will need to be followed up for safety (AEs) up to 30 days (+/- 5 days) after the last dose of avelumab and for disease progression / survival until the end of the trial (minimum of 12 months follow-up from the date of commencing treatment for the last patient).

If the patient stops trial treatment but has not progressed, they will be reviewed with a CT scan of neck, chest, abdomen and pelvis at 8, 12, 16 and 20 months or on clinical suspicion of progression (whichever is sooner).

If there is no evidence of progression after 20 months, patients will have no specific trial follow up, but their referring physician may be contacted every 6 months to determine progression and survival data.

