12.1.2 Secondary outcome measures

- Toxicity assessed using CTCAE v4.0 will be defined as the number and proportion of patients who experience one or more grade 3 or 4 adverse event or serious adverse event of any grade
- Best overall response (Partial Remission (PR) + Complete Response (CR)) at any time of treatment will be assessed using contrast-enhanced CT scans of the neck, chest, abdomen and pelvis, using the Revised Response Criteria for Malignant Lymphoma (²⁷)
- Maximum percentage change in the sum of the product of diameters (SPD) of target tumour masses assessed by contrast-enhanced CT scans of the neck, chest, abdomen and pelvis, using the Revised Response Criteria for Malignant Lymphoma²⁷
- Duration of response is defined as the time from first documented response until relapse/progression, as determined by the Revised Response Criteria²⁷, or death. Patients who are relapse/progression free and alive will be censored at date last seen.
- Progression free survival is defined as the time from date of registration to the date of disease progression or date of death from any cause. Patients not reaching progression or death at the time of analysis will be censored at the last date they were known to be alive and progression free. Patients will be followed up for a minimum of 12 months.
- Overall survival time is defined as the time from date of registration to the date of death from any cause. Patients discontinuing the study, lost to follow-up or still alive at the end of the study will be censored at the date of last follow-up. Patients will be followed up for a minimum of 12 months.

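### Maximum tumour shrinkage has no cut-off at new anticancer therapy, and the protocol does not require the start of such therapy to be recorded

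*Combined protocol and SAP*

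**What the plan says.** **Therapy after avelumab.** Section 7.7 limits its restrictions to one period: "Patients are prohibited from receiving the following therapies during the treatment phase of this trial". It closes with "There are no prohibited therapies during the Post-Treatment Follow-up Phase".

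**Scans after avelumab.** Section 7.9: "If the patient stops trial treatment but has not progressed, they will be reviewed with a CT scan of neck, chest, abdomen and pelvis". The time points are 8, 12, 16 and 20 months, or sooner if progression is suspected. Section 7.3.5 likewise keeps patients who have not progressed after 8 cycles on CTs at 12, 16 and 20 months from treatment start.

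**Outcome definitions.** Section 12.1.2 defines the tumour-size outcome as "Maximum percentage change in the sum of the product of diameters (SPD) of target tumour masses", assessed by CT. No end date is given. Section 12.2 summarises it as a mean with SD or a median with IQR, depending on the distribution. Duration of response and PFS end at relapse or progression, or death. For PFS, "Patients not reaching progression or death at the time of analysis will be censored at the last date they were known to be alive" and free of progression; duration of response is censored when the patient was last seen. Neither these definitions, section 12.2 nor Appendix 1 names new anticancer therapy or transplant as an event, a censoring point or a scan cut-off.

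**Recording.** The Table 2 row for concomitant diseases and treatment reads "Ongoing assessment until 28 days after treatment discontinuation". After 20 months, section 7.9 says only that "their referring physician may be contacted every 6 months to determine progression and survival data".

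**The concern.** Stopping without progression is foreseeable. Section 7.8 lists completion, toxicity and patient choice as reasons, Table 5 requires permanent discontinuation for several adverse events, and treatment beyond 8 cycles is optional (7.2). Such a patient may start another lymphoma treatment and still attend trial CTs. Because the SPD outcome takes the maximum over an open-ended series of scans, the deepest reduction wins, whichever treatment produced it. With one arm, nothing separates that shrinkage from the effect of avelumab.

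For duration of response and PFS, the issue is whether a reader can learn how far the estimates depend on later therapy. That needs a date which the protocol does not ask sites to supply.

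**Working it through.** **1. The plan's own figures.** The plan gives no figure for SPD change, duration of response or PFS. Its only design figures concern the response rate: P(rate > 35%) of 60% for 11/30 and 84% for 13/30. With a Beta(1,1) prior (assumed, since the parameters are not stated), 1 - BetaCDF(0.35; 1 + r, 1 + n - r) gives 60.3% and 84.1%. They reproduce, and they do not depend on this point.

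**2. Who is exposed.** Only patients who start new therapy before progression. Post-treatment trial scans are specified for patients who have not progressed, and PFS and duration of response have already ended in those who have. The documents give no rate for this group.

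**3. SPD change.** Assume one of 30 patients had a best change of 0% on avelumab and reaches -100% on later therapy.
- Shift in the mean = 100/30 = 3.3 percentage points; with 35 patients, 100/35 = 2.9.
- The median of 30 values is the average of the 15th and 16th, so one changed value moves it little.

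**4. PFS: what the choice of handling can do.** All inputs here are assumed. Of 30 patients, 18 have events by month 6, leaving 12/30 = 40.0%. At month 6, k of the remaining 12 start new therapy, and there are 4 more events by month 12.

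*Case A: all 4 later events are in patients without new therapy.*
- As written: 8/30 = 26.7% for every k.
- Censoring at new therapy: 0.40 × (12 - k - 4)/(12 - k).

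| k | As written | Censored at new therapy |
|---|---|---|
| 2 | 26.7% | 0.40 × 6/10 = 24.0% |
| 4 | 26.7% | 0.40 × 4/8 = 20.0% |
| 6 | 26.7% | 0.40 × 2/6 = 13.3% |

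*Case B: k = 4, and all 4 later events are in the patients who switched.*
- As written: 8/30 = 26.7%.
- Censored: 0.40 × 8/8 = 40.0%.

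Censoring lowers the estimate in case A and raises it in case B. Neither direction can be presumed.

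**5. Best overall response.** The primary outcome is confined to the first 8 cycles and the secondary version to the time on treatment. Section 7.7 prohibits other systemic anticancer therapy during the treatment phase, with palliative radiotherapy as an exception. Eight cycles last 8 × 28 = 224 days, about 7.4 months. If the 8-month CT of section 7.9 is counted from treatment start, it falls at about 243 days, some 19 days after that window closes.

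**The case against.** Four points can be made against raising this.

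- **Follow-up regardless of later therapy is a recognised approach.** This stands. A reader might infer that duration of response and PFS are wrongly defined, or biased in favour of avelumab. The documents do not support that: the definitions are coherent, and step 4 shows that censoring can move the estimate either way. If new therapy is started because the patient is worsening, censoring removes impending events. What remains is that the plan provides no sensitivity analysis and does not secure the date one would need.
- **The response endpoints are already bounded.** This also stands. A reader might infer that a response first seen at the 8-month CT on new therapy enters the primary outcome. The wording ties both response outcomes to treatment, and by day count the scan lies outside the 8-cycle window. Section 1.2.3 loosely speaks of 8 months of treatment, but that does not redefine the endpoint.
- **The data may exist or be obtainable.** The CRF is not among the documents; section 9.1 describes it only as covering treatment and outcome details, among other items. Forms can be changed without a protocol amendment, and sites continue to follow patients. It would therefore be too strong to say that later therapy goes unrecorded or that the problem could never be corrected. The supportable statement is that the protocol does not require the record.
- **Few patients, secondary outcomes.** Benefiting patients may continue avelumab, which shrinks the exposed group, and the only quantified activity criterion concerns the response rate. This limits the importance. It does not close the gap in the SPD definition.

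**Conclusion.** The point holds for maximum SPD change: read literally, the definition accepts shrinkage obtained on next-line therapy or after transplant. For duration of response and PFS it holds only as a missing requirement to record subsequent therapy and a missing sensitivity analysis. Best overall response is not shown to be affected.

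The size is unknown. The 3.3-point shift in a 30-patient mean is the effect of one assumed patient, not a forecast, and the PFS cases in step 4 use invented counts to show that handling can matter. This is a cheap improvement to secondary outcomes and does not bear on the trial's response-rate criterion.

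**What to change.** 1. **Sections 12.1.2 and 12.2:** limit maximum percentage change in SPD to scans before the first new anticancer therapy or transplant. State whether the palliative radiotherapy permitted by 7.7 counts as new therapy for this purpose. Scans during continued avelumab beyond cycle 8 stay in.
2. **Table 2 and section 7.9:** record the type and start date of the first subsequent anticancer therapy or transplant at the existing follow-up visits and the 6-monthly contacts.
3. **Section 12.2:** keep duration of response and PFS as written. Add for each a sensitivity analysis that censors at the last disease assessment before new therapy, with a note that this censoring may be informative and can move the estimate in either direction.

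The cost is one extra data item (type and date) at contacts that already take place, two extra Kaplan-Meier runs, and possibly a slightly less favourable SPD result. Clinical management is unchanged.
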